Measurements & Procedures	
 1. ALSFRS-R 2. SVC 3. MRC sum score 4. Hand-held Dynamometry 5. Motor cortex excitability by TMS 6. Plasma NfL levels 7. Blood: isolation nEVs and biomarker quantification (SOD1, Ataxin 2, C90rf72, UNC13A, TDP43, stathmin 2, NfL and NfH) 8. Brain MRI for neuronavigation 9. TPS stimulations (6 sessions of 20 min each in 2 weeks)
Study Product / Intervention	Neurolith is a medical device delivering transcranial pulse stimulations under neuronavigation guidance.
Controls	ALS patients allocated to sham stimulations. Sham treated patients will be offered to receive TPS therapy in the Open Label Extension phase (OLE) of the trial for ethical purposes.
Number of Participants & Rationale	
Stage 1: n=10
 
Stage 2: n=40 (randomization 2:1 active vs sham stimulation)
 
Rationale for sample size: this is an exploratory sample likely to be informative for experience in planning for future trials.

Study Duration:	
24 months
 
Stage 1: 6 months
 
Stage 2: 3 months recruitment, 6 months randomized phase, 6 months OLE, 3-month analysis and clinical scientific report

Timelines:	
Stage 1:
 
 ● First Patient First Visit (FPFV): September 1st, 2024 ● Last Patient Last Visit (LPLV): February 1st, 2025 
Stage 2:
 
 ● First Patient First Visit (FPFV): March 1st, 2025 ● Last Patient Last Visit (LPLV): October 1st, 2026
Study Schedule:	
Patients are recruited from the ALS center at Hospital del Mar from patients diagnosed with ALS and referrals provided by the local ALS foundation (Miquel Valls Foundation)
 
Stage 1: V1: informed consent, inclusion/exclusion criteria, TMS cortex excitability, brain MRI (for neuronavigation) can be conducted at any time between Visit 1 and 2; V2: stim; V3: TMS and biomarkers assessment week 4; V4: TMS and biomarkers assessment week 8.

	Stage 2: V1: informed consent, inclusion/exclusion criteria, TMS cortex excitability, brain MRI (for neuronavigation) can be conducted at any time between Visit 1 and 2; V2: randomization and baseline; V3-5: stim, biomarkers and scales; V6-V7: open label extension
Study Center:	ALS center and Neuromodulation center. Hospital del Mar – Pompeu Fabra University, Barcelona, Spain

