2.1 Trial Design

This is a pilot study for evaluating the efficacy of modulating the motor cortex (M1) with Transcranial Pulse Stimulation (TPS)^{2,3} delivered by NEUROLITH device in patients with sporadic Amyotrophic Lateral Sclerosis (ALS)⁴. TPS is aimed to reduce cortical hyperexcitability and slow disease progression of the upper motor pathway, which will reduce the neurodegeneration of the lower motoneuron pathway and delay clinical progression. We will include patients with diagnosis of sporadic ALS (definite or clinically probable) as defined by the World Federation of Neurology revised El Escorial criteria, slow vital capacity (SVC) of 50% or greater of estimated measure and presence of hyperexcitability in the motor cortex as demonstrated by transcranial magnetic stimulation (TMS). Patients 21 to 80 years old and male or female are eligible. Familial ALS is excluded from the study. Clinical adverse events and therapeutic effects will be assessed during the study. Considering the primary endpoint for stage 1 is the efficacy in reducing cortical hyperexcitability, the presence of M1 hyperexcitability at inclusion (baseline) is required. The study is composed of 2 stages: stage 1 is an open label study to assess the effects of TPS on biomarkers in ALS patients (TMS based hyper-excitability and molecular biomarkers); and stage 2 is a randomized, single blinded, sham controlled study to assess the efficacy of TPS in regulatory accepted clinical scales and biomarkers in patients with ALS.

Specific procedures to be performed during the trial, as well as their prescribed times and associated visit windows, are outlined in the Trial Flow Chart - Section 6.0. Details of each procedure are provided in Section 7.0 – Trial Procedures.

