3.0 OBJECTIVE(S) & HYPOTHESIS(ES)

3.1 Co- Primary Objective(s) & Hypothesis(es)

Objectives:

Stage 1. Change in the motor cortex excitability threshold from baseline to week 8.
 Stage 2. Change from baseline to month 6 in the ALS functional rating scale-revised (ALSFRS-R) total score.

Hypothesis:

TPS stimulation delivered to M1 will decrease cortical hyper-excitability and slow disease progression.

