4.2.2.1 Rationale for the Use of Sham

In order to assess the efficacy of the therapy in clinical outcomes, comparison between active and sham treatment is required. Using sham or placebo for 6 months is accepted for patients with ALS as shown in the most recent phase 2 and 3 trials. In order to encourage participation and fulfill patients' expectations, sham treated patients will receive active stimulation during the open label extension period (OLE), intended to collect more safety data and to assess sustainability of the efficacy observed in the double-blinded period (DBP).

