6.0 TRIAL FLOW CHART

Table 3 Trial flow chart

Stage 1 Visit Number	1	2	3-5	6
Visit Title	Screen	Baseline	Stimulation	End
Scheduled Week	0	1	2-3	4
Scheduling Window by Days:	3	3	2	5
Administrative Procedures				
Informed Consent	X			
Inclusion/Exclusion Criteria	X			
Identification Card	X			
Medical History	X			
Prior Medication Review	X			
Monitor Trial Device Compliance		X	X	
Clinical Procedures Assessments				
TPS stimulations	X	X	X	
Vital Signs		X	X	X
Physical Exam		X	X	X
MRC sum score		X	X	X
Hand-held dynamometry		X	X	X
Brain MRI		X		
TMS		X		
Neurological examination	X	X	X	X
C-SSRS	X	X	X	
ALSFRS-R	X	X	X	X
Blood draw		X	X	X
SVC		X		

Stage 2 Visit Number	1	2	3-5	6-7	8	9	10-16	17-18	19
Visit Title	Screen	Rand Base	Stim	Stim FU	End DBP	Onset OLE	Stim 3	Stim FU	End OLE
Scheduled Week	0	1	2-3	8-16	16	16	16-18	26-34	34
Scheduling Window by Days:	3	3	2	2	5	7	2	2	5
Administrative Procedures									
Informed Consent	X								
Inclusion/Exclusion Criteria	X								
Identification Card	X								
Medical History	X								
Prior Medication Review	X								
Monitor Trial Device Compliance		X	X	X			X	X	
Clinical Procedures Assessments									
TPS stimulations	X	X	X	X			X	X	
Vital Signs		X	X	X	X	X	X	X	X
Physical Exam		X	X	X	X	X	X	X	X
MRC sum score		X	X	X	X	X	X	X	X
Hand-held dynamometry		X	X	X	X	X	X	X	X
Brain MRI	X								
TMS	X	X	X	X	X				
Neurological examination	X	X	X	X	X	X	X	X	X
C-SSRS	X	X	X	X			X	X	
ALSFRS-R	X	X	X	X	X	X	X	X	X
Blood draw		X	X	X	X				
SVC		X				X			

Stim: TPS stimulation (6 times in 2 weeks, 20 min each); rand: randomization; Base: baseline; DBP: double blind period; OLE: Open Label Extension

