7.1.5.1 Visits

Each visit should be performed as noted in the Trial Flow Chart. For visits that require additional explanations, please see those specific visits below.

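### The Stage 2 flow chart closes the blinded period at week 16, so a trial run from it obtains no sham-controlled value at month 6, when the primary and secondary endpoints are due

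*Protocol*

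**What the plan says.** Several parts of the protocol set a six-month blinded comparison:

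- Section 3.1 gives the primary endpoint as "Stage 2. Change from baseline to month 6 in the ALS functional rating scale-revised (ALSFRS-R) total score". Sections 1.0, 8.1 and 8.4.1 repeat it. Section 3.2 sets the Stage 2 secondary endpoints at month 6 too: slow vital capacity (SVC), plasma NfL, TMS excitability, MRC sum score and dynamometry.
- The study duration in Section 1.0 is "Stage 2: 3 months recruitment, 6 months randomized phase, 6 months OLE, 3-month analysis and clinical scientific report".
- Section 4.2.2.1 defends the length of the control period: "Using sham or placebo for 6 months is accepted for patients with ALS".
- The power statement (Sections 1.0, 8.1 and 8.9) refers to week 24.

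The Stage 2 chart in Section 6.0 differs. Baseline is at week 1. From the blinded follow-up sessions onward, the scheduled weeks read "8-16 16 16 16-18 26-34 34". In column order these are the follow-up sessions, end of the double-blind period (Visit 8), OLE onset (Visit 9), the OLE stimulation course, the OLE follow-up sessions and the end of the OLE.

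The protocol makes this chart the working schedule. Section 2.1 says that for the trial procedures "their prescribed times and associated visit windows, are outlined in the Trial Flow Chart", and Section 7.1.5.1 says "Each visit should be performed as noted in the Trial Flow Chart".

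**The concern.** The endpoint and the schedule cannot both be followed. A centre that books visits from the chart closes the blinded period about two months before the primary endpoint is due and then offers active stimulation to the sham patients. A randomised comparison against sham at month 6 cannot be recovered once those patients have been treated. ALSFRS-R at about six months would then compare earlier with later TPS, which is not the question in Section 3.1. A statistical analysis plan cannot repair this, because the data would not exist.

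**Working it through.** **Inputs.** All weeks and windows come from the Stage 2 chart in Section 6.0: baseline week 1 (3-day window), end of double-blind period week 16 (5-day window), OLE onset week 16, OLE course weeks 16–18, OLE follow-up weeks 26–34, end of OLE week 34. The nine entries in the week row match the nine visit columns, so the text extraction has not shifted them. A month is taken as 30.44 days, so six months is 26.1 weeks. Month 6 is shown for 24 and 26 weeks.

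**Charted blinded follow-up.** 16 − 1 = 15 weeks; 15 × 7 / 30.44 = 3.4 months. This is 15/24 = 62.5% or 15/26 = 57.7% of the intended period.

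**Windows.** With baseline 3 days early and Visit 8 5 days late, follow-up is 15 + 8/7 = 16.1 weeks.

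**Where month 6 falls.** 1 + 24 = chart week 25, or 1 + 26 = chart week 27. That is 9 or 11 weeks after the charted end of the blinded period.

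**Charted OLE.** 34 − 16 = 18 weeks; 18 × 7 / 30.44 = 4.1 months, against six.

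**Which side is wrong.** The Trial Outline total is 6 + 3 + 6 + 6 + 3 = 24 months, as stated. With the charted periods it is 6 + 3 + 3.45 + 4.14 + 3 = 19.6 months. In the chart, the last follow-up session and the end of the period share a week in both phases (16 and 34). The chart therefore appears to stop each phase at its last session and to omit the remaining time.

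**What is available near month 6, by endpoint:**

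- *ALSFRS-R, MRC, dynamometry:* the nearest charted visit is Visit 17, taken as week 26. It is 26 − 1 = 25 weeks (5.7 months) after baseline, but also 26 − 18 = 8 weeks after the OLE course ends.
- *SVC:* charted only at Visit 2 (week 1) and Visit 9 (week 16).
- *TMS and blood:* the last charted collection is Visit 8 (week 16).
- *Section 7 additions:* Section 7.1.3.1 adds NfL after stimulation sessions and at the end of the OLE. Section 7.1.5.1.3 adds TMS, blood and ALSFRS-R at the close of each six-session course. On the charted timing, any such sample near month 6 follows OLE treatment.

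No endpoint has a sham-controlled month-6 value.

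**The case against.** The strongest defence is that the six-month intent is stated many times, so the chart is a clerical slip that staff would notice. The intent is indeed clear, and the harm is conditional on the chart being followed. But Sections 2.1 and 7.1.5.1 send staff to the chart, and Section 7 gives no week for the end of the blinded period that would correct it. The Stage 2 diagram is not visible in the text reviewed and is not relied on here.

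A reader might infer more than the document supports:

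- *That TMS is never collected around month 6.* Section 7.1.5.1.3 also lists Visits 22–28, which may be a second OLE course with TMS at its close. It gives no weeks, so such a measurement could fall at or after month 6. It would still follow OLE treatment, so only the absence of a sham-controlled value is claimed.
- *That month-6 data would be unblinded.* Nothing says that allocation codes are opened at OLE onset. The sound objection is that sham patients in the OLE have received active TPS.
- *That visit counts show too few sessions.* This assumes one session per visit. Section 7.1.4.1 implies three stimulations within Visit 2, while Section 7.1.5.1.2 describes one. The text is unclear and shows no deficit.
- *That the calendar has months to spare.* That rests on "Last Patient Last Visit (LPLV): October 1st, 2026". Twenty-four months from 1 September 2024 end about 1 September 2026, analysis included, so this date conflicts with the stated total.
- *That power is lost by a known amount.* The power statement gives no effect size, standard deviation or sidedness, so no such figure can be derived.

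**Conclusion.** The contradiction stands and must be corrected before the schedule is used. As charted, blinded follow-up is 15 weeks instead of about 24 to 26, and the OLE is 18 weeks instead of six months. Followed literally, the chart leaves the Stage 2 primary endpoint and the month-6 secondary endpoints without a sham-controlled measurement.

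This rests on two assumptions: that visits are booked from the chart, as the protocol directs, and that sham patients take up the active stimulation provided for in the OLE. The arithmetic is certain. That the chart, and not the endpoint, is the error is an inference, strongly supported by the Trial Outline durations, the sham rationale and the power statement.

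**What to change.** Amend the Stage 2 chart in Section 6.0:

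1. Move the end of the double-blind period and OLE onset to 24 weeks after baseline, chart week 25. The only week figure the protocol attaches to this comparison is week 24. If the sponsor means 26 weeks, the chart week is 27; one week must be stated.
2. At that time point, take ALSFRS-R, SVC, TMS, blood, MRC and dynamometry before any OLE stimulation.
3. Keep the blinded sessions at months 2 and 4.
4. Shift the OLE columns by 9 weeks (course 16–18 becomes 25–27; follow-up 26–34 becomes 35–43). End the OLE six months after onset: 25 + 24 = about week 49.
5. Align the visit numbers in Sections 1.0 and 7.1.5.1 with the corrected chart. Section 1.0 now has "V6-V7: open label extension", while the chart starts the OLE at Visit 9 and Section 7.1.5.1 uses numbers up to 29.

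The cost is a protocol amendment, with no extra patients and no new type of assessment. Week 49 is 49 × 7 / 30.44 = 11.3 months after screening, within the 6 + 6 months per patient that Section 1.0 already plans.

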3.2 Key Secondary Objective(s) & Hypothesis(es)

Objectives:

Secondary stage 1:

1. Change in the motor cortex excitability from baseline to week 4
2. Change plasma NfL levels from baseline to week 4 and 8
3. Changes in muscle strength, assessed by MRC sum score from baseline to week 4 and 8
4. Changes in hand-held dynamometry from baseline to week 4 and 8

Secondary stage 2:

1. Differences (treated vs sham) and change (from baseline to end of the study (month 6)) in the slow vital capacity (SVC)
2. Differences (treated vs sham) and change (from baseline to end of the study (month 6)) in plasma NfL levels or other biomarkers from exploratory stage 1 if found significant
3. Differences (treated vs sham) and change (from baseline to end of the study (month 6)) in cortical hyperexcitability (MEP amplitudes, resting motor threshold, ICF and SICI)
4. Changes in muscle strength, assessed by MRC sum score from baseline to end of the study (month 6)

5. Changes in hand-held dynamometry, from baseline to end of the study (month 6)

Hypothesis:

TPS stimulation delivered to M1 will decrease cortical hyper-excitability and slow disease progression.

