7.1.2.2.4 SVC

The slow vital capacity (SVC) is the volume of air expired through an unforced maneuver measured by spirometry. SVC of 50% or greater of estimated measure is required to participate in the study.

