7.1.5.1.1 Visit 1: Screening, brain MRI, TMS and SVC

At Visit 1, subjects who provide informed consent will undergo a series of diagnostic and safety assessments to determine if they are eligible for the trial. A designated subject must also consent to participate and will be asked to complete certain assessments throughout the trial. Subjects planning to undergo elective procedures during the study (known prior to trial start) should not proceed until such procedures have been completed.

At the screening visit, medical history, use of drugs, alcohol, caffeine, smoking will be recorded. In addition urine test and the Columbia-Suicide Severity Rating Scale (C-SSRS) will be administered. The SVC will be collected by spirometry.

If the subject fulfills the inclusion criteria and signs the informed consent, a brain MRI and a TMS study will be scheduled in the following 2-7 days (always before Visit 2). Once obtained the brain MRI, it will be uploaded to the TPS device for neuronavigation purposes. TMS will be conducted for defining presence of hyper-excitability.

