7.1.5.1.3 Visit 3-5, 6-12, 15-21 and 22-28: stimulation visits

At each visit the patient will be reassessed for vital signs, physical exam and neurological exam. After the completion of each 6-session period, the C-SSRS will be administered. Blood and urine will be collected the last day of stimulation for each 6-session period. TMS and ALSFRS-R will be assessed the last day of stimulation for each 6-session period.

7.1.5.1.2 Visit 13, 14 and 29: end of stage 1, end of DBP, onset and end of OLE of stage 2

During such visits, vital signs, physical exam, and neurological exam and ALSFRS-R will be conducted.

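### The only post-baseline SVC in Stage 2 is charted at the onset of the open-label extension, not at the end of the blinded period, so this secondary endpoint is not assured for patients who do not continue

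*Protocol*

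**What the plan says.** **Endpoint.** Section 3.2 (repeated in Sections 1.0, 4.2.3.1, 8.1 and 8.4.1) puts SVC first among the Stage 2 secondary endpoints: "Differences (treated vs sham) and change (from baseline to end of the study (month 6)) in the slow vital capacity (SVC").

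**Entry criterion.** Section 7.1.2.2.4 states: "SVC of 50% or greater of estimated measure is required to participate in the study". The text on Visit 1 (Section 7.1.5.1.1) has SVC in its heading and says: "The SVC will be collected by spirometry".

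**Schedule.** The Stage 2 chart in Section 6.0 has the columns "Visit Title Screen Rand Base Stim Stim FU End DBP Onset OLE Stim 3 Stim FU End OLE" and "Scheduled Week 0 1 2-3 8-16 16 16 16-18 26-34 34". Its SVC row carries a mark at Visit 2 and at Visit 9, and nowhere else.

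**Visit text.** For the end of the blinded period and the onset and end of the extension, Section 7.1.5 says: "During such visits, vital signs, physical exam, and neurological exam and ALSFRS-R will be conducted". SVC is not in that list.

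**Extension.** Section 1.0 states: "Sham treated patients will be offered to receive TPS therapy in the Open Label Extension phase (OLE) of the trial for ethical purposes". Section 4.2.2.1 adds that the extension should also show whether efficacy seen in the blinded period is sustained.

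**The concern.** A treated-versus-sham comparison at the end of the blinded period needs its outcome measured in every randomised patient at the visit that closes that period. For SVC the chart attaches the measurement to the visit that opens the extension. Entry to the extension is offered, and no section guarantees that every randomised patient attends its opening visit.

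In a progressive disease, the patients who stop after the blinded period may be those with worse respiratory function, and their share may differ by arm. If so, the patients with an SVC outcome would be a selected subset of those randomised. The analysis cannot repair this fully, because a measurement that was never scheduled cannot be recovered.

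A smaller matter sits beside it. SVC decides eligibility, and the chart and the text disagree on whether it is taken at Screening.

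**Working it through.** **1. The chart rows side by side (Section 6.0, Stage 2).**

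| Measure | Visit 1, Screen (wk 0) | Visit 2, Rand/Base (wk 1) | Visit 8, End DBP (wk 16) | Visit 9, Onset OLE (wk 16) | After Visit 9 |
|---|---|---|---|---|---|
| SVC | – | X | – | X | – |
| TMS | X | X | X | – | – |
| Blood draw | – | X | X | – | – |
| MRC sum score | – | X | X | X | X |
| Dynamometry | – | X | X | X | X |
| ALSFRS-R | X | X | X | X | X |

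The SVC row has as many fields as the header row (10 and 10). The neighbouring rows fall in sensible columns, so a shift of the SVC row alone in the extracted text is unlikely. Every other Stage 2 secondary measure is charted at Visit 8; SVC is the exception. TMS and blood stop at Visit 8, while MRC and dynamometry continue to Visit 19.

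**2. Whether the text fills the gap.** The list for the end-of-period and extension visits omits SVC. It also omits TMS, blood, MRC and dynamometry, so it is not exhaustive, and its silence alone proves little. But for those four measures the chart supplies Visit 8, and for SVC it does not. Section 7.1.4.1, on withdrawal, refers only to activities scheduled for the end of Visit 2. Section 5.8 allows some patients to stop treatment and still be monitored, but not to restart it. Nothing says that such patients attend the opening visit of a treatment extension.

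**3. Number exposed.** Stage 2 has 40 patients. The protocol gives no rate of non-entry, so the following range is an assumption:

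- 10%: 0.10 × 40 = 4 patients
- 30%: 0.30 × 40 = 12 patients

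**4. What that could do to the comparison.** Let p be the fraction of an arm without an end-of-period SVC, and Δ the mean SVC change in patients with a value minus the mean in those without. The observed arm mean then differs from the full arm mean by p × Δ, and the treatment difference is off by

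bias = p(active) × Δ(active) − p(sham) × Δ(sham).

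With the same Δ in both arms, equal fractions give no bias, while 0.30 against 0.10 gives (0.30 − 0.10) × Δ = 0.20 Δ. The documents give no value for Δ, so the bias cannot be put in SVC units.

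Precision suffers less. If the loss is proportional in both arms, the standard error grows by 1/√0.90 = 1.05 at 10% and 1/√0.70 = 1.20 at 30%.

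**5. Timing.** Six months is 6 × 365.25/12/7 = 26.1 weeks. Week 16 is 16 × 7/(365.25/12) = 3.7 months, or 3.4 to 3.9 months across the 7-day window at Visit 9. The charted SVC therefore falls about 10 weeks before month 6, whether or not a patient enters the extension. This mismatch also affects the other Visit 8 measures and must be resolved for the whole schedule.

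**6. Eligibility.** Section 7.1.5.1.1 takes SVC at Visit 1. The chart leaves Visit 1 blank and marks Visit 2. Section 7.1.1.9 has patients randomised once eligibility is confirmed at Visit 2.

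**The case against.** The strongest reply is that Visits 8 and 9 are both scheduled in week 16 and the visit text treats them together with one list of assessments. Nothing limits Visit 9 to patients entering the extension. If everyone attends both visits, SVC is obtained near the close of the blinded period and little is lost. Patients who die or withdraw before week 16 miss Visit 8 as well, so moving the tick would not recover them. All of this stands. It confines the gap to patients who reach Visit 8 and do not attend Visit 9. It does not close the gap, because a visit named for the onset of the extension is not assured for someone who does not continue.

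Three stronger readings are tempting and are not supported:

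- A reader might infer that non-entrants definitely have no SVC outcome. The chart fails to assure one; it does not rule one out.
- A reader might infer from the offer to sham patients that mainly they enter, so that nearly the whole active arm loses its SVC. Section 4.2.2.1 gives the extension the further aim of assessing sustained efficacy, which suggests that active patients continue too.
- A reader might infer that patients can be randomised before the 50% criterion is checked. The Visit 1 text collects SVC, and Section 7.1.1.9 places confirmation of eligibility before randomisation. What remains is a contradiction between chart and text.

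It can also be said that this is a secondary endpoint in a convenience-sample pilot that Section 8.1 describes as descriptive. That limits the weight of the point, but a descriptive comparison between arms is distorted by selective missingness in the same way.

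**Conclusion.** The point holds as a scheduling defect. The first Stage 2 secondary endpoint has its only post-baseline measurement at the onset of the extension and none charted at the visit that ends the blinded period.

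The number affected is unknown: 4 to 12 of 40 under the assumed 10-30% non-entry, and none if every patient who completes Visit 8 also attends Visit 9. Bias is possible, not established. It requires that non-entry be related to SVC decline and that the resulting distortion differ between arms, and the protocol informs neither condition.

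The blank at Visit 1 is a separate inconsistency between chart and text. The change should be made because it protects a named endpoint at almost no cost; the primary endpoint is not touched by this point, since ALSFRS-R is charted at Visit 8.

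**What to change.** In the Stage 2 flow chart:

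- Move the SVC tick from Visit 9 to Visit 8 (End DBP), and state that it applies to all randomised patients whether or not they enter the extension.
- Reconcile the timing of that visit, now week 16, with the month-6 endpoint.
- Tick SVC at Visit 1, to agree with Section 7.1.5.1.1.

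Add SVC to the text for the end-of-blinded-period visit so that chart and text agree. That text numbers its visits 13, 14 and 29, while the chart has 8, 9 and 19 for the end of the blinded period and the onset and end of the extension; the numbering can be aligned in the same edit.

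The cost is a flow-chart amendment and a line of text. One spirometry moves between two visits of the same scheduled week, and the Visit 1 spirometry is already in the protocol text.
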